11.2. Appendix II: Selection of OBP Values at Follow-Up

The analysis windows are defined as follows:

Study Visit	Target Date (post procedure)	Protocol Defined Window (post procedure)	Expanded Analysis Window (post procedure)
1 Month	30	23-37	14-60
3 Months	90	76-104	61-135
6 Months	180	166-194	136-270
12 Months	360	330-390	271-540

Scenario 1: There are multiple ABPM raw data records with the same ABPM CPEVENT including SV2:

1. Starting with the most recent ABPM raw record, is there any OBP visit (SCHEDULED or UNSCHEDULED) where 'OFFICE follow up BP date' = 'ABPM start date'?
2. If yes, then use that OBP visit if it is in the expanded analysis window.
3. If no, then go to the previous ABPM raw record, and again look for any OBP visit (SCHEDULED or UNSCHEDULED) where 'OFFICE follow up BP date' = 'ABPM start date'. If yes, then use that OBP visit if it is in the expanded analysis window. In no, then go to the previous ABPM raw record...
4. Repeat for all ABPM raw records.

Scenario 2: There is only 1 ABPM raw data record for a given CPEVENT:

This scenario only applies to the follow up measurements in the table above. SV2 and discharge measurements will still use site reported values. In case of multiple measurements for discharge, then take the latest one.

1. Time to follow up will be calculated as (follow up BP date – procedure date). Only SCHEDULED follow up data will be included.
2. All follow up measurements <14 days post procedure will not be included in the follow up analysis unless otherwise specified.
3. The remaining measurements will be categorized per windows defined above. In case of multiple qualifying measurements, first take the one closest to the target follow up date, then take the latest one.

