- **Renal artery imaging** will be performed at the 6-month follow-up visit to assess if a renal artery stenosis is suspected. A renal duplex ultrasound (DUS) will be obtained at 6-months follow up and submitted to the DUS Core Laboratory. If the DUS is determined to be nondiagnostic a repeat DUS, a MRA, CT or angiogram will be performed (repeat imaging is to be completed within 30 days after confirmation of non-diagnostic imaging). If evidence of a clinically significant stenosis is indicated by the DUS or MRA/CT Core Laboratory, an angiogram must be obtained and submitted to the angiographic core laboratory.
  - If renal imaging is not obtained at the 6-month follow-up visit due to extenuating circumstances, renal imaging is required at the next scheduled study visit.
- **24-hour ABPM** will be conducted at the 3, 6, and 12-month follow-up visits post-procedure according to the guidelines in **Appendix 16.5**. A repeat ABPM will be required in the event of technical issues, failure to follow ABPM guidelines or if the minimum required number of daytime and nighttime readings is not obtained. If ABPM is repeated office blood pressure and drug testing (for 3-month follow up only) must be repeated on day the ABPM is applied.
  - Initiate medication re-Introduction for subjects with systolic OBP  $\geq 140$  mmHg at 3-month follow-up visit. Starting at the 3-month follow up after clinical assessment and a valid ABPM are completed.
- **Mortality assessment** will be completed by the investigational site when a subject cannot be reached after each of the protocol required follow-up visits.
- **Drug testing** (urine/blood) to ensure medications are no longer present in the subject's system. A urine sample will be collected, preferably using the subject's first morning urine. A blood sample will be collected at the time of the visit. Drug testing samples collected for subjects that screen fail after obtaining the sample, must not be sent to the core lab for analysis.

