Alternative methods of data collection may be necessary in the case of extenuating circumstances, such as a global pandemic, when subjects are prohibited from coming into the office for required assessments. For all assessments completed via alternative methods in these circumstances, sites are not required to enter a protocol deviation for missing, and/or alternative data collection. Data unable to be collected remotely or via an alternative method should be collected at the next possible in-person visit. In the event a subject is unable to return for an in-office follow-up visit, the alternative methods of obtaining follow-up assessments are listed below:

In-home visit by trained and delegated site personnel or designee, for example, home health care personnel. The following assessments may not be completed with an in-home visit:

- **Renal artery imaging:**
  - Make every effort to schedule in-person renal artery imaging as soon as possible.
  - When possible, the subjects may be referred to a local imaging center for assessment. Local imaging technicians would require study training and delegation prior to assessment.

Virtual visit, inclusive of video with study subject, or a phone visit.

The following assessments may **not** be completed with a virtual visit or a phone visit:

- **Clinical assessment:** limited review to be completed per physician discretion.
- **Laboratory tests:**
  - When possible, the subject should be referred to a local laboratory to collect samples. Laboratory kits to be provided to subjects in advance of the visit by study site.
- **Renal artery imaging:**
  - Make every effort to schedule in-person renal artery imaging as soon as possible.
  - When possible, the subjects could be referred to a local imaging center for assessment. Local imaging technicians would require study training and delegation prior to assessment.
- **Office blood pressure and ABPM** units to be provided to the subjects in advance of the visit by the study site. Measurements collected by the subject may be collected and designated as subject-reported in the CRF.
  - Witnessed pill intake prior to ABPM, if applicable.
  - Documentation of pill intake will be assessed virtually or as confirmed verbally by subject.

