11.3. Appendix III: Selection of ABPM Values at Follow-Up

The analysis windows are defined as follows:

Study Visit	Target Date (post procedure)	Protocol Defined Window (post procedure)	Expanded Analysis Window (post procedure)
3 Months	90	76-104	46-135
6 Months	180	166-194	136-270
12 Months	360	330-390	271-540

1. This algorithm only applies to the follow up measurements in this table. SV2 measurements will still use site reported values. If there are multiple SV2 measurements per subject, the most recent one will be taken.
2. ABPM start date will be used as follow up date.
3. Time to follow up will be calculated as (ABPM start date – procedure date); Only SCHEDULED follow up data will be included in this analysis; If there are multiple measurements per subject per site reported visit (CPEVENT), the most recent one will be taken before applying the expanded analysis window algorithm below.
4. All follow up measurements <46 days post procedure will not be included in the follow-up analysis unless otherwise specified.
5. The remaining measurements will be categorized per windows defined above. In case of multiple qualifying measurements, first take the one closest to the target follow up date, then take the latest one.

This document is electronically controlled. Printed copies are considered uncontrolled.

Confidential

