11.4. Appendix IV: Derivation of ABPM Values

1. The ABPM raw data will be entered into the database by data management team. The following steps will be done by SAS programming team:
2. Missing values for the NUM field will be deleted as they do not contain BP data.
3. Manual readings are identified by the text "Start of a manual measurement" in the BPNOTE field in the raw data file.
4. Readings after 7:00am and before 10:00pm (7:00am \leq time $<$ 10:00pm) are daytime readings; readings after 10:00pm and before 7am next day (time \geq 10:00pm or time $<$ 7:00am) are nighttime readings.
5. Keep all the non-manual readings and all the manual readings that are after the non-manual readings.
6. The initial manual readings (all the manual readings before the first non-manual reading) will be handled as following:
 - Starting from the last initial manual reading and compare it with the reading immediately after that, if it is more than ($>$) 30 minutes before the next reading, then all the manual readings will be removed; if it is within (\leq) 30 minutes before the next reading, then move to the second last manual reading and compare it with the reading immediately after that.
 - Repeat this until all the manual readings are included or some manual readings are excluded.

This step can be demonstrated with the examples below:

Reading #	Reading type	Example 1	Example 2	Example 3
1	M	12:00pm	12:00pm	12:00pm
2	M	12:30pm	12:31pm	12:30pm
3		1:00pm	1:00pm	1:01pm

In Example 1, all the readings will be kept.

In Example 2, only readings 2 and 3 will be kept.

In Example 3, only reading 3 will be kept.

7. Truncate all the readings that are more than ($>$) 25 hours after the remaining first reading.

The overall, daytime and nighttime ABPM will be calculated based on the remaining raw data. Only measurements with at least 21 daytime and 12 nighttime readings will be used for 24 hours ABPM analysis. Only measurements with at least 21 daytime readings will be used for daytime ABPM analysis. Only measurements with at least 12 nighttime readings will be used for nighttime ABPM analysis.

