11.5. Appendix V: Selection of Lab Values at Follow-Up

The analysis windows are defined as follows:

Study Visit	Target Date (post procedure)	Protocol Defined Window (post procedure)	Expanded Analysis Window (post procedure)
1 Month	30	23-37	14-60
3 Months	90	76-104	61-135
6 Months	180	166-194	136-270
12 Months	360	330-390	271-540

Scenario 1: There are multiple ABPM raw data records with the same ABPM CPEVENT including SV2:

1. Starting with the most recent ABPM raw record, is there any Lab visit (SCHEDULED or UNSCHEDULED) where 'Lab follow up date' = 'ABPM start date'?
2. If yes, then use that Lab visit if it is in the expanded analysis window.
3. If no, then go to the previous ABPM raw record, and again look for any Lab visit (SCHEDULED or UNSCHEDULED) where 'Lab follow up date' = 'ABPM start date'. If yes, then use that Lab visit if it is in the expanded analysis window. In no, then go to the previous ABPM raw record...
4. Repeat for all ABPM raw records.

Scenario 2: There is only 1 ABPM raw data record for a given CPEVENT:

This algorithm only applies to the follow up measurements in the tables above. SV2 will still use site reported values. In case of multiple SV2 measurements, then take the latest one. Date of specimen collection will be used as lab follow up date.

1. Time to follow up will be calculated as (lab follow up – procedure date). Only SCHEDULED follow up data will be included in this analysis.
2. All follow up measurements <14 days post procedure will not be included in the follow up analysis unless otherwise specified.
3. The remaining measurements will be categorized per windows defined above. In case of multiple qualifying measurements, first take the one closest to the target follow up date, then take the latest one.

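### When a follow-up ABPM is repeated, the SAP's selection rules have no rule for some cases, so a usable in-window office BP, lab, drug test or ABPM value can be lost (minor)

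*SAP*

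**What the plan says.** SAP Appendix II has two routes for choosing the office BP of a visit. The first opens with "Scenario 1: There are multiple ABPM raw data records with the same ABPM CPEVENT including SV2". It starts from the latest ABPM record and looks for an office BP dated on the ABPM start date. If one exists, the instruction is "If yes, then use that OBP visit if it is in the expanded analysis window". If none exists, it moves to the previous ABPM record, and it closes with "Repeat for all ABPM raw records". Scenario 2 applies only when the visit has a single ABPM record. It takes scheduled measurements in the expanded window, nearest to the target day and then the latest.

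Appendix V has the same structure for labs ("If yes, then use that Lab visit if it is in the expanded analysis window"), and Appendix VI has it for drug testing.

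For the ABPM itself, Appendix III item 3 restricts to scheduled data and says that, with several measurements under one visit label, "the most recent one will be taken before applying the expanded analysis window algorithm below". The adequacy rule is in Appendix IV: "Only measurements with at least 21 daytime and 12 nighttime readings will be used for 24 hours ABPM analysis". Daytime and nighttime analyses each have their own count there. Neither appendix says which of the two runs first.

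Protocol 9.1.6 adds: "If ABPM is repeated office blood pressure and drug testing (for 3-month follow up only) must be repeated on day the ABPM is applied". Labs are not named in that sentence. SAP 7.3 rules out imputation of missing outcomes.

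**The concern.** Repeating an ABPM switches the visit from Scenario 2 to Scenario 1, which is stricter and has no last step. A scheduled, in-window reading that would have been used after a single ABPM can then go unused only because the ABPM was repeated. In Appendix III, choosing the latest recording before looking at the window lets a late repeat displace an earlier usable recording.

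A lost office BP or 24-hour value drops out of the 3-month comparison with SPYRAL HTN-OFF MED. That comparison spreads about 50 DYSTAL subjects over five strata, about 50/5 = 10 in each. A lost 3-month drug test could bear on per-protocol membership. The undefined steps also matter for reproducibility: SAP section 8 has two programmers working independently, and the text allows them to reach different values from the same data.

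**Working it through.** **Inputs.**
- Expanded windows for office BP and labs: 3 months = days 61-135, 6 months = days 136-270 (Appendices II and V).
- Expanded windows for ABPM: 3 months = days 46-135, 6 months = days 136-270 (Appendix III). Drug testing at 3 months: days 46-135 (Appendix VI).
- Target days: 90 and 180.
- About 50 treated subjects.

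**Scenario 1 as written.** Take ABPM days from latest to earliest. If a record exists on that day and lies in the window, select it. If it exists but lies outside the window, the text is open: the search may stop, because the next step is reached only when no same-day record exists, or it may continue, because the closing step says to go through all records.

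| 3-month case (constructed dates) | Search stops | Search continues | Scenario 2 rule |
|---|---|---|---|
| ABPM 90 and 100; only office BP day 91 | none | none | day 91 (61 ≤ 91 ≤ 135) |
| ABPM 90 and 98; only lab day 92 | none | none | day 92 |
| ABPM and office BP both on 100 and 137 | none (137 > 135) | day 100 | day 100 |
| ABPM and office BP both on 90 and 100 (protocol-compliant) | day 100 | day 100 | not needed |

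The Scenario 2 column assumes that the reading is coded as scheduled.

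**Appendix III as written**, with all recordings scheduled and under the 3-month label:

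| Recordings | Select, then check adequacy | Check adequacy, then select |
|---|---|---|
| Day 100 adequate, day 137 adequate | day 137, moved to 6 months | day 137, moved to 6 months |
| Day 90 adequate, day 100 inadequate | none | day 90 |
| Day 90 inadequate, day 100 adequate (usual case) | day 100 | day 100 |

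In the first row the 3-month value is lost on either reading. Day 137 lies in 136-270, so it becomes a 6-month candidate at |137 − 180| = 43 days from target. Any 6-month recording nearer to day 180 then replaces it.

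**Size.** The documents give no rate of repeats or of date mismatches. As an assumption only: if 10-20% of visits have a repeated ABPM, and in 10-30% of those no lab falls on an ABPM date, the loss is 50 × 0.10 × 0.10 = 0.5 to 50 × 0.20 × 0.30 = 3 subjects per visit.

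**Precision.** SAP section 6 quotes a drop of 5.5 mmHg in 38 subjects, 95% CI −9.1 to −2.0, p = 0.003. The standard error is (9.1 − 2.0)/2 ÷ t(0.975, 37 df) = 1.75, so t = 3.14 and p = 0.0033, which agrees with the quoted p. The standard deviation is 1.752 × √38 = 10.8. If DYSTAL has that SD, the half-width of the 95% CI for the mean change is 3.07 mmHg with 50 subjects and 3.24 with 45. A few lost values cost little precision.

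**Check on the fallback.** The 4-month visit falls at about 4 × 30 = 120 ± 7, that is days 113-127, which is inside 61-135. Under Protocol 9.1.10 it follows medication re-introduction. An unrestricted fallback could therefore take an on-medication office BP as the 3-month off-medication value.

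**The case against.** The strongest reply is that repeats done as the protocol says lose nothing. Protocol 9.1.6 requires office BP and, at 3 months, drug testing on the day of the repeat, so a same-day record should exist. A lab drawn with the first ABPM is found when the search steps back. Appendix 16.5.3 asks for repeats until enough readings are obtained, so the latest recording is normally the adequate one. Protocol 9.1.7 treats a return for a repeat ABPM as unscheduled. If the repeat is coded that way, Appendix III ignores it and no displacement arises. All of this stands, and it is why the loss is possible rather than routine. It does not supply the missing steps. Scenario 1's own trigger, several records under one visit label, shows that the SAP expects repeats to be stored that way.

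Stronger readings that a reader might infer, and that the documents do not support:
- That Appendix III selects before checking adequacy. The order is unstated, and checking first fits the text equally well.
- That the search must stop at an out-of-window match. This is the literal branch, but the closing step can be read as continuing.
- That labs are often drawn on other days. The sentence "When possible, the subject should be referred to a local laboratory to collect samples" covers virtual or phone visits in extenuating circumstances and says nothing about the day. It makes a mismatch plausible, no more.
- That a lost creatinine counts as no event. SAP 7.7.1 builds its numerator on CEC-adjudicated events, and the creatinine endpoint is not adjudicated. Nothing says that this endpoint uses the single value chosen by Appendix V. Protocol 9.1.8 separately requires a confirmatory draw and an adverse event report if the rise is confirmed.

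**Conclusion.** The concern holds in a limited form, for follow-up visits only. Two defects are in the text: Scenario 1 has no rule when no same-day record exists, and Appendix III applies the window after taking the latest recording. Two further steps are undefined rather than wrong: what follows an out-of-window match, and when the reading-count check is made. A usable in-window value can be lost as a result, and it then stays missing.

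The number affected cannot be derived from the documents. The illustrative 0.5 to 3 subjects per visit rests on assumed rates and should not be cited as a finding. The worked cases are atypical: the office BP case needs a departure from the same-day requirement, and the days 100 and 137 case needs a repeat after a recording that already met the count. Severity is minor. The reason to act is that the loss is avoidable, the rules should be reproducible, and the change is nearly free.

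**What to change.** For follow-up visits only, leaving SV2 out because the windows are all post-procedure:

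1. Appendices II, V and VI, Scenario 1: search from the latest ABPM back for a same-day record that lies inside the expanded window, and continue past any match outside it.
2. If none is found, apply the Scenario 2 rule to records of the same visit label (CPEVENT). For the 3-month value, exclude any office BP taken after antihypertensive medication was restarted. Flag the value in the listing.
3. Appendix III item 3: handle the 24-hour, daytime and nighttime analyses separately. For each, first keep recordings that meet that analysis's own Appendix IV count, fall in the window, and were not rejected for a technical fault or failure to follow ABPM instructions. Then take the most recent. A single 21/12 filter for all three would discard recordings that Appendix IV keeps for daytime-only or nighttime-only analysis.

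On the worked cases this gives office BP day 91, lab day 92 and, for days 100 and 137, the day-100 ABPM and office BP.

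The cost is a few sentences in the SAP and a small programming change, with no new data. Step 3 relies on the recorded reason for a repeat. The downside is that a fallback office BP or lab may come from a different day than the ABPM, hence the flag.

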11.3. Appendix III: Selection of ABPM Values at Follow-Up

The analysis windows are defined as follows:

Study Visit	Target Date (post procedure)	Protocol Defined Window (post procedure)	Expanded Analysis Window (post procedure)
3 Months	90	76-104	46-135
6 Months	180	166-194	136-270
12 Months	360	330-390	271-540

1. This algorithm only applies to the follow up measurements in this table. SV2 measurements will still use site reported values. If there are multiple SV2 measurements per subject, the most recent one will be taken.
2. ABPM start date will be used as follow up date.
3. Time to follow up will be calculated as (ABPM start date – procedure date); Only SCHEDULED follow up data will be included in this analysis; If there are multiple measurements per subject per site reported visit (CPEVENT), the most recent one will be taken before applying the expanded analysis window algorithm below.
4. All follow up measurements <46 days post procedure will not be included in the follow-up analysis unless otherwise specified.
5. The remaining measurements will be categorized per windows defined above. In case of multiple qualifying measurements, first take the one closest to the target follow up date, then take the latest one.

This document is electronically controlled. Printed copies are considered uncontrolled.

Confidential

11.4. Appendix IV: Derivation of ABPM Values

1. The ABPM raw data will be entered into the database by data management team. The following steps will be done by SAS programming team:
2. Missing values for the NUM field will be deleted as they do not contain BP data.
3. Manual readings are identified by the text "Start of a manual measurement" in the BPNOTE field in the raw data file.
4. Readings after 7:00am and before 10:00pm (7:00am \leq time $<$ 10:00pm) are daytime readings; readings after 10:00pm and before 7am next day (time \geq 10:00pm or time $<$ 7:00am) are nighttime readings.
5. Keep all the non-manual readings and all the manual readings that are after the non-manual readings.
6. The initial manual readings (all the manual readings before the first non-manual reading) will be handled as following:
 - Starting from the last initial manual reading and compare it with the reading immediately after that, if it is more than ($>$) 30 minutes before the next reading, then all the manual readings will be removed; if it is within (\leq) 30 minutes before the next reading, then move to the second last manual reading and compare it with the reading immediately after that.
 - Repeat this until all the manual readings are included or some manual readings are excluded.

This step can be demonstrated with the examples below:

Reading #	Reading type	Example 1	Example 2	Example 3
1	M	12:00pm	12:00pm	12:00pm
2	M	12:30pm	12:31pm	12:30pm
3		1:00pm	1:00pm	1:01pm

In Example 1, all the readings will be kept.

In Example 2, only readings 2 and 3 will be kept.

In Example 3, only reading 3 will be kept.

7. Truncate all the readings that are more than ($>$) 25 hours after the remaining first reading.

The overall, daytime and nighttime ABPM will be calculated based on the remaining raw data. Only measurements with at least 21 daytime and 12 nighttime readings will be used for 24 hours ABPM analysis. Only measurements with at least 21 daytime readings will be used for daytime ABPM analysis. Only measurements with at least 12 nighttime readings will be used for nighttime ABPM analysis.

